#### **7.3.2 Safety**

The name and address of each third party vendor (eg, clinical laboratory) used in this study will be maintained in the investigator's and sponsor's files.

Actual safety assessment times will be monitored and recorded. The sponsor's expectation is that the investigator will ensure that every effort is made to perform all assessments at the precise protocol-scheduled time. Unless otherwise noted, any safety assessment that deviates from the scheduled assessment time set forth in the protocol by more than  $\pm 15$  minutes will be considered a protocol deviation.

AEs (defined as AEs occurring from the time of informed consent signature to first dose of investigational product), TEAEs (all AEs occurring after the first treatment), prior medication and concomitant medication use will be assessed and monitored from the time the subject signs the informed consent form to completion of study (including to time of screen failure or drop out/discontinuation). While confined in the CRC, subject safety will also be closely monitored through blood pressure measurements, ECG measurement, clinical safety labs and physician oversight.

In the event anti-PTH antibodies are detected following analysis for a subject, the investigator will be notified by the Sponsor. It will be the investigator's responsibility to notify the subject.

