### 11.1 Adverse Events

Adverse events will be coded using Version 19.0 or newer of MedDRA.

An AE (classified by preferred term) that occurs during the study will be considered a TEAE if it has a start date/time on or after the first dose of investigational product or if it has a start date before the date of the first dose of investigational product, but increases in severity on or after the date/time of the first dose of investigational product. If more than 1 AE with the same preferred term is reported before the date of the first dose of investigational product, then the AE with the greatest severity will be used as the benchmark for comparison to the AEs occurring during the study under the preferred term. An AE that occurs more than 5 days (120 hours) after the last dose of investigational product will not be counted as a TEAE.

Adverse events will be assigned to a treatment as follows. If the onset date of the AE is after first dose in Period 1, but prior to first dose in Period 2, and is  $\leq 5$  days after the date of last dose in Period 1 it will be counted as a Period 1 AE. If the onset date of the AE is after first dose in Period 2, and is  $\leq 5$  days after the date of last dose in Period 2 it will be counted as a Period 2 AE. Period 1 AEs will be assigned to the treatment received in Period 1, and Period 2 AEs will be assigned to the treatment received in Period 2. AEs with onset date  $> 5$  days after the last dose in Period 1 and prior to the first dose in Period 2 will be counted as a Washout AE, not assigned to a treatment, and not considered a TEAE. AEs with onset date  $> 5$  days after the last dose in Period 2 will be counted as a Follow-up AE, not assigned to a treatment, and not considered a TEAE.

When summarizing non-TEAEs by treatment, AEs occurring prior to first dose in Period 1 will be excluded, and other non-TEAEs will be assigned to the last treatment received.

An overall summary of the number of subjects with AEs will be presented by treatment and overall, including the number and percentage of subjects with any AEs, serious AEs, AEs related to investigational product, AEs leading to discontinuation of investigational product, severe AEs, and deaths. The number and percentage of subjects with TEAEs and non-TEAEs will be presented for the same categories.

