## **17. CHANGES TO ANALYSES SPECIFIED IN PROTOCOL**

There were no changes to the analysis planned in the latest version of the protocol.

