#### **Missing/Incomplete Time**

If the time is missing and the date is complete and is the same as the date of the first dose of investigational product in either period, or the date is imputed to be one of these dates, then

the time will be set to the time of the first dose of investigational product on that day. Otherwise, missing times will be imputed as 00:00.

If the minutes are given but the hour is not, then the time will be regarded as completely missing and handled as above. If the hour is given but the minutes are not, then if the hour is the same as the hour of a dose of investigational product on that day, then the minutes of that dose of investigational product will be assigned to the missing fields. Otherwise 00 will be assigned to the missing minutes.

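### SAP 11.1 treats an AE at the exact first-dose time as treatment-emergent but assigns it to no period, and the SAP's imputation rules place AEs at exactly that time

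*SAP*

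**What the plan says.** SAP 11.1 puts an AE into a treatment column in two steps.

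- **TEAE status.** An AE qualifies if "it has a start date/time on or after the first dose of investigational product" (or if an earlier event worsens from then on). There is an upper limit: "An AE that occurs more than 5 days (120 hours) after the last dose of investigational product will not be counted as a TEAE".
- **Period, and so treatment.** Period 1 applies "If the onset date of the AE is after first dose in Period 1, but prior to first dose in Period 2", provided onset is no more than 5 days after the last Period 1 dose. The Period 2 rule opens "If the onset date of the AE is after first dose in Period 2" and has the same 5-day condition. Later onsets become Washout or Follow-up AEs, which carry no treatment and are not TEAEs.

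The next paragraph of 11.1 covers by-treatment summaries of non-TEAEs. Events before the first Period 1 dose are left out, and "other non-TEAEs will be assigned to the last treatment received".

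SAP 18.6.1 handles incomplete AE start dates by reference to 18.5.1. Under 18.5.1, if the time is missing and the date is (or has been imputed to be) a first-dose date in either period, "the time will be set to the time of the first dose of investigational product on that day".

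Protocol 7.3.2 describes the events more widely, as "TEAEs (all AEs occurring after the first treatment", with no upper time limit. SAP 17 states: "There were no changes to the analysis planned in the latest version of the protocol".

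**The concern.** The TEAE rule includes equality with the first-dose time. The two assignment rules exclude it. That would not matter if exact equality were rare, but the SAP's own imputation creates it. Resolving doubtful timing to the moment of dosing looks intended to count the event against that period's treatment. The assignment wording then defeats that intention.

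Safety and tolerability is the secondary objective, and SAP 11.1 tabulates TEAEs by treatment, including the special-interest events hypercalcemia, hypocalcemia and hypercalciuria. A TEAE without a treatment has no column in those tables. It would still meet the TEAE definition for the overall column of the summary table, so the columns might not reconcile.

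**Working it through.** The plan states no figure to reproduce here. The check is to apply the rules literally.

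**Notation.** t1 and t2 are the first-dose times in Periods 1 and 2. L1 and L2 are the last-dose times.

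**Rules from SAP 11.1.**
- TEAE: onset ≥ t1, and no more than 120 h (5 × 24) after the latest dose.
- Period 1: onset > t1, onset < t2, onset no more than 5 days after L1.
- Period 2: onset > t2, onset no more than 5 days after L2.
- Washout: onset more than 5 days after L1, and before t2.
- Follow-up: onset more than 5 days after L2.

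**How imputation under SAP 18.5.1 reaches t1 or t2.**
- Complete date equal to a first-dose date, time missing: set to the first-dose time.
- Day missing, month and year those of the first dose: set to the first-dose date, then to its time. A date in a later month that is the month of the Period 2 dose goes to the Period 2 first dose.
- Day and month missing: the dosing year leads to the first-dose date in the same way.
- Hour given, minutes missing, hour equal to that of the first dose: takes the minutes of that dose. An hour-only onset in the evening BID dose hour takes the evening dose time. That is later than the first dose, so it is assigned normally.

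**Schedules tested (hours, t1 = 0).**
- QD then BID, 30-day washout: L1 = 0, t2 = 720, L2 = 732.
- BID then QD, 30-day washout: L1 = 12, t2 = 720, L2 = 720.
- BID then QD, 5-day washout: L1 = 12, t2 = 120, L2 = 120.

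| Onset | TEAE? | Class as written | Class with *on or after* |
|---|---|---|---|
| t1 | yes | none | Period 1 |
| t1 + 1 h | yes | Period 1 | Period 1 |
| t2 | yes | none | Period 2 |
| t2 + 1 h | yes | Period 2 | Period 2 |
| L1 + 121 h, 30-day washout | no | Washout | Washout |
| L1 + 121 h, 5-day washout | yes | Period 2 | Period 2 |
| L2 + 121 h | no | Follow-up | Follow-up |

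Rows that name no washout gave the same result in all three schedules. An onset at t2 fails Period 1 because it is not before t2, and fails Period 2 because it is not later than t2. It also fails Washout and Follow-up. With *on or after*, both boundary events are assigned once, and no other tested event changes class.

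**Effect of one lost subject.** Each cohort needs at least 8 completers. Treatments A, C, D and F each come from one cohort: 1/8 = 12.5 percentage points. Treatments B and E each come from two cohorts: 1/16 = 6.25 points. These apply to a row in which the subject has no other event.

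**The case against.** The strongest reply is that this is an equality sign. Any programmer would read *after* as *on or after*, and nothing in the SAP says to drop these events. SAP 18.6 speaks of incomplete dates, so a complete date with a missing time is reached only through the reference to 18.5.1. Subjects are confined from Day -2 to Day 2, so few dosing-day AEs should lack a time. All AEs are listed.

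Much of this stands, and it limits the size. It does not remove the gap. The sensible reading is an unwritten repair, and partial dates reach the first-dose time whichever way 18.6 is read. The text also says onset *date*. Compared as dates, even a timed dosing-day AE would not be later than the dosing date, so that reading is no rescue.

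A reader might infer four stronger points that the documents do not support.

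- *That 11.1 has two opposite rules for events later than 5 days.* The last-treatment sentence is confined to by-treatment summaries of non-TEAEs, so it can sit alongside the Washout and Follow-up classes. What is left open is narrower: which rule governs by-treatment tables that mix both kinds, namely 4.2.1 and 4.5.3.
- *That late events vanish from the tables.* SAP 11.1 repeats the summaries for non-TEAEs, and the table list in SAP 20 includes by-treatment non-TEAE tables.
- *That most safety information is lost.* Between 23/33 = 70% of post-dose days (5-day washout, follow-up at 28 days, BID then QD) and 52/62.5 = 83% (30-day washout, follow-up at 32 days, QD then BID) fall outside the TEAE window. These are calendar shares, not event counts, and do not measure impact.
- *That the protocol's definition must be the primary one.* Protocol 9.4 leaves safety-analysis definitions to the SAP, and Protocol 9.9 does not define a TEAE. The 5-day window matches the minimum washout. With no limit and last-treatment assignment, a Period 1 treatment would be observed for 5 to 30 days and a Period 2 treatment for 28 days or more.

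**Conclusion.** The assignment wording is wrong as written. A TEAE whose onset equals a first-dose time has no period and no treatment, and the SAP's imputation produces such onsets. The finding rests on reading the two sets of rules literally and on 18.6.1 carrying the time rules of 18.5.1 across to AEs. It also assumes that onset times are collected, as the SAP's start date/time wording implies.

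The number of affected events cannot be derived from the documents and is probably small. Confinement makes missing times unlikely. It protects less against partial dates for events recalled from washout or follow-up. The consequence is limited to by-treatment TEAE counts in a descriptive study. No event leaves the listings.

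Two lesser documentation gaps remain: the unstated rule for Tables 4.2.1 and 4.5.3, and a TEAE window narrower than Protocol 7.3.2 that SAP 17 does not declare. The SAP may set the window, but it should say that it differs from the protocol.

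**What to change.** In SAP 11.1, change the opening condition of both assignment rules to *on or after first dose in Period x*. Keep the requirement that a Period 1 onset precede the Period 2 first dose, and keep the limit of 5 days after the last dose in both rules.

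As clean-up:

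- State in 11.1 that the last-treatment rule for AEs later than 5 days also governs the by-treatment columns of Tables 4.2.1 and 4.5.3.
- Record in SAP 17 that the 5-day window narrows the TEAE definition in Protocol 7.3.2.

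The cost is a few lines of SAP text and a comparison operator in the programs. Data collection, study conduct and the primary TEAE window do not change.

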On Day 1 of Treatment Period 2, subjects will receive the alternative treatment (according to the randomization schedule), following a washout period ( $\geq 5$  days [ie, 120 hours] and  $\leq 30$  days) between administration of the dose or first dose ([for once-daily or twice-daily dosing, respectively] of each treatment period). All investigational product will be administered via SC injection into alternating thighs at each administration.

At each treatment period, subjects will report to the CRC on Day-2, remain in the CRC through Day 2, and be discharged following the last scheduled assessment on Day 2 (investigators may elect, at their discretion, to keep the subject in-clinic after Treatment Period 1 for the duration of the washout period, eg, if the washout period is short [eg, 120-172 hours] or there are any safety concerns).

For once-daily treatments (Treatments B and E), subjects will receive a single subcutaneous dose of rhPTH(1-84) in the morning on Day 1. For twice-daily treatments (Treatments A, C, D, and F), subjects will receive a subcutaneous dose of rhPTH(1-84) in the morning followed by the second dose 12 hours later on Day 1 (in the opposite thigh). If randomized to rhPTH(1-84) with calcium, subjects will take their usual supplemental oral calcium on Day 1 per their usual schedule. Prior to discharge from the CRC at each treatment period, subjects will be given specific instructions for when to take their supplemental oral calcium and active vitamin D supplements during the day(s) when subjects are not in the CRC.

Subjects enrolled in the study must require daily doses of calcium supplements of  $\geq 1000$  mg prior to baseline (Day 1). Subjects enrolled in the study must also require minimum daily doses of active vitamin D of  $\geq 0.25\mu\text{g}$  (ie,  $0.25\mu\text{g}$  calcitriol or equivalent). Subjects will be expected to adhere to standard meals provided during their confinement in the CRC during each period (from check-in on Day -2 until discharge on Day 2). All subjects (in all treatments) will take their usual doses at the usual regimen of supplemental oral calcium and active vitamin D on Day -2 and Day -1. For all subjects in all cohorts, active vitamin D supplements must be withheld on Day 1 through completion of all study procedures on Day 2. Subjects may resume active vitamin D following final procedures on Day 2 at the discretion or direction of the investigator.

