## 9.9 Safety Analyses

Adverse events will be coded using the Medical Dictionary for Regulatory Activities. The number of events, incidence, and percentage of treatment-emergent adverse events will be calculated overall, by system organ class, by preferred term, and by treatment group. Treatment-emergent AEs will be further summarized by severity and relationship to investigational product. Adverse events related to investigational product, AEs leading to withdrawal, SAEs, and deaths will be similarly summarized/listed.

Safety data including clinical laboratory tests, anti-PTH antibodies, concomitant medications, adverse events, ECG monitoring and vital signs assessments will be summarized by treatment and time of collection. Descriptive statistics (arithmetic mean, standard deviation, median, minimum and maximum) will be calculated for quantitative safety data as well as for the difference from baseline, if applicable. Frequency counts will be compiled for classification of qualitative safety data.

Safety will be assessed by the following evaluations:

- AEs and TEAEs (including episodes of hypocalcemia and/or hypercalcemia [including paresthesia, numbness, tetany] and hypercalciuria)
- Laboratory test results (hematology, serum chemistries, creatinine clearance, urinary chemistries (24-hr urinary calcium, sodium, citrate, phosphate, cAMP, magnesium and creatinine excretion), immunology (anti-PTH antibody), and urinalysis)
- ECG
- Physical examinations (including vital signs)

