The number and percentage of subjects reporting TEAEs for each treatment will be tabulated by system organ class (SOC) and preferred term; by SOC, preferred term, and maximum severity. TEAEs considered related to investigational product will also be summarized by SOC and preferred term. If more than 1 AE occurs with the same preferred term for the same subject, then the subject will be counted only once for that preferred term using the most severe and most related occurrence for the summarization by severity and by relationship to investigational product. Severe TEAEs, Serious TEAEs and TEAEs leading to discontinuation of investigational product will be summarized by SOC, preferred term and treatment.

A summary table of TEAEs of special interest will be produced showing the number and percentage of subjects reporting TEAEs of special interest for each treatment tabulated by preferred term. The TEAEs of special interest are hypercalcemia, hypocalcemia and hypercalciuria.

The above summaries will be repeated for non-TEAEs. A separate summary of all AEs of special interest (including TEAEs and non-TEAEs) will also be produced.

Listings will be produced for all AEs (including pre-treatment AEs), SAEs, AEs considered related to investigational product, AEs leading to discontinuation of investigational product, deaths, and AEs of special interest.

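### SAP 11.1 omits the number of treatment-emergent adverse events that Protocol 9.9 specifies, and SAP 17 does not declare the departure

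*SAP*

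**What the plan says.** Protocol 9.9 names three statistics for TEAEs: "The number of events, incidence, and percentage of treatment-emergent adverse events will be calculated overall, by system organ class, by preferred term", and the sentence goes on to add treatment group. The number of events is listed separately from incidence and percentage.

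SAP 11.1 defines its adverse event summaries in terms of subjects:
- Overall table: "An overall summary of the number of subjects with AEs will be presented by treatment and overall".
- By system organ class and preferred term: "The number and percentage of subjects reporting TEAEs for each treatment will be tabulated by system organ class (SOC) and preferred term".
- Special interest (hypercalcemia, hypocalcemia, hypercalciuria): a table "showing the number and percentage of subjects reporting TEAEs of special interest for each treatment tabulated by preferred term".
- Repeats: "then the subject will be counted only once for that preferred term using the most severe and most related occurrence". The rest of that sentence ties the choice of occurrence to the severity and relationship summaries.

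For severe and serious TEAEs, related TEAEs and those leading to discontinuation, SAP 11.1 does not name the statistic. No adverse event table title in SAP 20 mentions a number of events. SAP 17 reads: "There were no changes to the analysis planned in the latest version of the protocol".

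Under Protocol 3.1, QD subjects receive one injection per period. BID subjects receive one "in the morning followed by the second dose 12 hours later on Day 1 (in the opposite thigh").

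**The concern.** The protocol promises a statistic that the SAP does not provide for, and the SAP section meant to record such departures says there are none.

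The omission matters somewhat more here than in a parallel-group trial with one dose schedule. Safety and tolerability form the secondary objective, and the study rationale (Protocol 2.1) is to characterise twice-daily dosing beside once-daily. With two injections in one arm of the crossover and one in the other, a natural descriptive question is whether a reaction happens once or comes back after the second injection. A count of subjects cannot answer that; a count of events read against exposure partly can.

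**Working it through.** The documents state no adverse event rate and no power-based sample size, so there is no figure to reproduce. The check is a comparison of texts, followed by an illustration of what the two statistics show.

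**1. Texts side by side.** Protocol 9.9: events, incidence, percentage. SAP 11.1: number and percentage of subjects wherever a statistic is named. SAP 20: no event count in any title. SAP 17: no change. The first and last cannot both be right on the SAP's text.

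**2. Within one treatment column.** Inputs: 8 subjects on a BID treatment (the planned minimum per cohort) and 2 injections each. Suppose k subjects have the same preferred term.
- Once each: subjects k, events k.
- After both injections: subjects k, events 2k.

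For k = 4, both cases print as 4/8 (50.0%), while events are 4 or 8. The same holds for k = 1, 2 and 8 (12.5%, 25% and 100%). This is the information lost.

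**3. Across columns.** The adverse event tables are by treatment. Treatment B is taken in Cohorts 1 and 2 and Treatment E in Cohorts 3 and 4. SAP 12.3.4 splits B and E by cohort for pharmacokinetics only. At minimum size a BID column has 8 subjects and 8 × 2 = 16 administrations; a QD column has 8 + 8 = 16 subjects and 16 × 1 = 16 administrations. In the limiting case where every injection produces the event:

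| | BID column | QD column |
|---|---|---|
| Subjects with event | 8/8 (100%) | 16/16 (100%) |
| Events | 16 | 16 |
| Events per subject | 16/8 = 2.0 | 16/16 = 1.0 |
| Events per administration | 16/16 = 1.0 | 16/16 = 1.0 |

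The raw event totals are equal. The difference appears only after dividing by subjects exposed, and the per-injection rate is the same. An event column therefore needs its denominators.

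**4. When repeats do not cluster.** Assume events are independent between injections with per-injection risk p (assumed values). The expected number of BID subjects with an event is 8 × [1 − (1 − p)²]; per 8 QD subjects it is 8p.

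| p | BID subjects | QD subjects (per 8) | BID events | QD events (per 8) |
|---|---|---|---|---|
| 0.1 | 1.52 | 0.8 | 1.6 | 0.8 |
| 0.2 | 2.88 | 1.6 | 3.2 | 1.6 |
| 0.3 | 4.08 | 2.4 | 4.8 | 2.4 |
| 0.5 | 6.0 | 4.0 | 8.0 | 4.0 |

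Here subject counts do rise under BID, so the masking is confined to repeats of one preferred term in the same subject.

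**5. What a raw count would include.** Protocol 8.1.1 has each change of severity recorded as a new event. One episode that worsens once yields two records and would look like a recurrence unless the records are linked.

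**The case against.** The strongest reply is that little is lost. SAP 11.1 lists every adverse event (Listing 7.1) and every event of special interest (Listing 7.6), and SAP 8.1 lists dose dates and times. With about 8 subjects per cohort, a reader can find recurrences by hand. The study is descriptive. Table specifications sit in a separate document (SAP 1) that is not available here, and most of the adverse event tables are marked as sponsor standard, so the shells may already carry an event column. All of that stands as a limit on the consequence. It does not meet the protocol's commitment to calculate the number of events by treatment, which listings do not total, and it does not make the SAP 17 statement correct.

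A reader might infer three stronger things:
- That the tables hide a 2:1 excess of events under BID. They do not: with B and E pooled over two cohorts, the limiting case gives 16 events in each column, and BID and QD percentages coincide only when reactions repeat within the same subjects.
- That the SAP deliberately removed event counts. The SAP is silent; it nowhere says that counts will not appear.
- That the protocol's count would show whether events recur after the second dose. A total carries no timing, and neither document plans a split around that dose.

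**Conclusion.** The point holds as a protocol-to-SAP inconsistency with a limited consequence. Protocol 9.9 specifies the number of TEAEs, SAP 11.1 specifies subjects only, and SAP 17 is incorrect in declaring no change. The summary tables as described cannot show recurrence of one preferred term within a subject and period.

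The text conflict needs no assumption about event rates. The practical loss depends on how often such repeats occur, which the documents do not allow one to estimate; the figures above are illustrations at the minimum cohort size. The conclusion rests on the SAP text, since the table shells cannot be seen. No primary pharmacokinetic or pharmacodynamic result is affected.

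**What to change.** 1. In SAP 11.1, add the number of events beside n (%) in the overall table (4.2.1), the SOC/preferred-term tables (4.2.2, 4.2.3) and the special-interest tables (4.5.1 to 4.5.3), by treatment and overall.
2. State that records created by a change in severity of one episode count as one event, and say how such records are linked.
3. Show the numbers of subjects and administrations exposed, already tabulated under SAP 8.1, with the counts, and note that raw totals are not comparable between the BID columns and the pooled B and E columns.
4. Correct SAP 17 if any departure from Protocol 9.9 remains. If the shells already contain an event column, one sentence in SAP 11.1 plus the linking rule is enough.

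A split of BID onsets before and after the second dose is optional and would be a new analysis. It should use recorded onset times only: SAP 18.6.1 applies the rules of 18.5.1, under which a missing time on the date of a period's first dose is set to the time of that dose, which would push such events into the earlier interval.

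Cost: one added column in tables already planned, and a rule for linking severity-change records that the documents do not yet contain. No new data collection is needed for the count itself.

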**Safety Endpoints:**

Safety will be assessed by the following evaluations:

- AEs including episodes of hypocalcemia, hypercalcemia, and hypercalciuria
- Laboratory test results (hematology, serum chemistries, creatinine clearance, urinary chemistries (24-hr urinary calcium, sodium, citrate, phosphate, cAMP, magnesium, and creatinine excretion), immunology (anti-PTH antibody), and urinalysis

- ECG
- Physical examinations (including vital signs).

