## 8. ADVERSE AND SERIOUS ADVERSE EVENTS ASSESSMENT

### 8.1 Definition of Adverse Events, Period of Observation, Recording of Adverse Events

An AE is any untoward medical occurrence in a clinical investigation subject administered a pharmaceutical product and that does not necessarily have a causal relationship with this treatment. An AE can therefore be any unfavorable and unintended sign (including an abnormal laboratory finding), symptom, or disease temporally associated with the use of a medicinal (investigational) product, whether or not related to the medicinal (investigational) product (ICH Guidance E2A 1995).

All AEs are collected from the time the informed consent is signed until the defined follow-up period stated in Section 7.2.4. This includes events occurring during the screening phase of the study, regardless of whether or not investigational product is administered. Where possible, a diagnosis rather than a list of symptoms should be recorded. If a diagnosis has not been made, then each symptom should be listed individually. All AEs should be captured on the appropriate AE pages in the CRF and in source documents. In addition to untoward AEs, unexpected benefits outside the investigational product indication should also be captured on the AE CRF.

All AEs must be followed to closure (the subject's health has returned to his/her baseline status or all variables have returned to normal), regardless of whether the subject is still participating in the study. Closure indicates that an outcome is reached, stabilization achieved (the investigator does not expect any further improvement or worsening of the event), or the event is otherwise explained. When appropriate, medical tests and examinations are performed so that resolution of event(s) can be documented.

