### 8.1.4 Symptoms of the Disease under Study

Symptoms of the disease under study should not be classed as AEs as long as they are within the normal day-to-day fluctuation or expected progression of the disease and are part of the efficacy data to be collected in the study; however, significant worsening of the symptoms should be recorded as an AE.

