## **10. EFFICACY ANALYSES**

No efficacy analysis will be performed for this study.

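### The SAP's special-interest tables count three terms only, so calcium episodes recorded as a symptom or a laboratory term fall outside them, although Protocol 9.9 includes the symptoms

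*SAP*

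**What the plan says.** Protocol 9.9 lists among the safety evaluations "AEs and TEAEs (including episodes of hypocalcemia and/or hypercalcemia [including paresthesia, numbness, tetany] and hypercalciuria". The protocol synopsis, under Safety Endpoints, gives a shorter form without symptoms: "AEs including episodes of hypocalcemia, hypercalcemia, and hypercalciuria".

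SAP 11 names clinical episodes of hypocalcemia and hypercalcemia, and hypercalciuria, as safety variables alongside AEs and TEAEs. It gives no case definition. SAP 11.1 then provides a special-interest table by preferred term and treatment: "The TEAEs of special interest are hypercalcemia, hypocalcemia and hypercalciuria". SAP 20 lists it as Table 4.5.1, with Table 4.5.2 for non-TEAEs and Table 4.5.3 for both together. SAP 17 states: "There were no changes to the analysis planned in the latest version of the protocol".

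Two recording rules in the protocol bear on what reaches these tables. Section 8.1 asks for a diagnosis where possible and adds: "If a diagnosis has not been made, then each symptom should be listed individually". Section 8.1.4 begins: "Symptoms of the disease under study should not be classed as AEs as long as they are within the normal day-to-day fluctuation" (or expected progression), and continues with a second condition and a limit: "are part of the efficacy data to be collected in the study; however, significant worsening of the symptoms should be recorded as an AE". SAP 10 states: "No efficacy analysis will be performed for this study".

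**The concern.** Protocol 9.9 treats three named symptoms as part of a calcium episode. The SAP keeps the idea of a clinical episode but drops the symptoms at the point where episodes are counted, and does not say so. Events of this kind are a central tolerability question in a trial that withholds active vitamin D in all cohorts and oral calcium in two of them. If the special-interest tables are read as the count of calcium episodes per treatment, they can understate it. With at least 8 subjects per cohort, one or two subjects would visibly change the table.

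Protocol 8.1.4 adds a separate ambiguity. Protocol section 1 names numbness, paresthesias and tetany among the key symptoms of hypocalcemia in this disease, so the exemption is aimed at the same symptoms that 9.9 counts. One of its two conditions refers to efficacy data, and this study plans no efficacy analysis.

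**Working it through.** The plan gives no figure to reproduce. The check is a comparison of the texts, plus the weight of one subject.

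**1. Where each kind of event lands.** This applies Protocol 8.1 for recording and SAP 11.1 and SAP 20 for tabulation.

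| Event after dosing | Recorded as | Table 4.2.2 and Listing 7.1 | Table 4.5.1 |
|---|---|---|---|
| Tingling, diagnosed as hypocalcemia | hypocalcemia | yes | yes |
| Tingling, no diagnosis made | paresthesia | yes | no |
| Low calcium value judged an AE (Protocol 8.1.5) and recorded as a laboratory finding | for example, blood calcium decreased | yes | no |
| Tingling and tetany in one subject, no diagnosis | two symptom terms | yes, in two rows | no |

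The table assumes onset in the treatment-emergent window. Tables 4.5.2 and 4.5.3 use the same three terms.

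**2. Whether the general tables can replace the missing count.** SAP 11.1 counts a subject once per preferred term. In the last case above the subject appears in two rows, so adding rows does not give the number of subjects with any calcium episode. The laboratory PCI criteria in SAP 11.2 include 24-hour urine calcium but no serum calcium limits, so there is no PCI count of low or high serum calcium either.

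**3. Whether a symptom-only record can arise.** PD serum samples are shipped frozen (Protocol 7.3.4.2). Safety biochemistry in each treatment period is drawn after the last serial sample on Day 2 (Protocol Table 1, note g). It goes to a central laboratory, with a local immediate test as an option (Protocol 7.3.2.5). A diagnosis supported by a calcium value on Day 1 therefore depends on the site ordering a local test. The documents do not say how often that will happen.

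**4. Weight of one subject.** One subject changes an incidence by 1/n.
- Treatments A, C, D and F, one cohort each at the minimum size: n = 8, and 1/8 = 12.5 percentage points.
- Treatment B (Cohorts 1 and 2) and Treatment E (Cohorts 3 and 4): n = 8 + 8 = 16, and 1/16 = 6.25 percentage points.

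Because 8 is a minimum, a larger cohort makes the change smaller.

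**5. Protocol 8.1.4.** The exemption needs two things together: the symptom is within normal fluctuation or expected progression, and it is part of the efficacy data. The protocol's endpoints are pharmacokinetic, pharmacodynamic and safety, and the SAP plans no efficacy analysis. On its wording the second condition is not met, so the symptoms remain recordable. A site could still treat the calcium-control objective as efficacy and apply the exemption. The schedule contains no symptom diary that would catch what is not recorded as an AE.

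**The case against.** The strongest reply is that nothing recorded disappears. The Protocol 9.9 evaluation is AEs and TEAEs as a whole. Every TEAE is tabulated by system organ class, preferred term and treatment, and every AE is listed. Protocol 9.9 does not ask for a grouped episode count. This stands, and it answers a reading that a reader might infer, namely that the symptoms are lost from the safety endpoint. They are missing only from the special-interest tables.

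A reader might also infer that Protocol 8.1.4 permits sites to leave such symptoms unrecorded. It does not: both conditions must hold, significant worsening is recorded in any case, and AEs are asked about at each visit (Protocol 7.3.2.3). What remains is a risk that unclear wording is misapplied.

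A third inference would be that withholding supplements biases the treatment comparison. Each randomized crossover pairs treatments with the same supplement status (A with B, C with B, D with E, F with E), so withholding gives no reason for uneven recording between the once-daily and twice-daily regimens. Only the non-randomized contrast across cohorts could be affected, and the documents give no evidence that it is.

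Two further points have some force. The synopsis names the same three conditions as the SAP, and the bracket in 9.9 can be read as describing how an episode presents rather than as stand-alone terms. The SAP introduction also places table specifications in a separate document, which may contain term groupings. Neither removes the gap: the SAP makes clinical episodes a safety variable and must say which records count as one.

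**Conclusion.** The mismatch is real and worth correcting before database lock. The special-interest tables are narrower than Protocol 9.9, SAP 11 leaves clinical episodes undefined, and SAP 17 does not acknowledge the difference. The consequence is a possible undercount in the only adverse-event tables that gather calcium events by treatment: 12.5 points per affected subject at n = 8, and 6.25 points in pooled B or E. The number of affected subjects cannot be derived from the documents. The rates in Protocol 1.3 (24 of 121 with post-treatment hypocalcemia, 29 of 121 with hypercalcemia) show that such events are not rare, but they say nothing about how events are coded.

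The conclusion assumes that the three names in SAP 11.1 are applied as preferred terms and that no unseen specification widens them. Safety is a secondary, descriptive objective without hypothesis testing, and serum calcium is summarized separately by treatment and time point. This is a moderate reporting gap, not a threat to the primary objective.

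**What to change.** **SAP 11.1, before database lock.** Replace the three names by a prespecified list of preferred terms for each category, following Protocol 9.9. For the calcium categories, include paresthesia, numbness (hypoesthesia), tetany, and blood calcium decreased or increased; for hypercalciuria, urine calcium increased. Count subjects with any term in the category, once each, and keep the three-term count as a sub-row. Apply the same list to Tables 4.5.1 to 4.5.3 and use it to define clinical episodes in SAP 11. Fixing the list in advance avoids choosing terms after seeing open-label data. If the sponsor prefers the narrower set, SAP 17 should declare it.

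**Protocol 8.1.4.** State that the exemption does not apply in this study because no efficacy data are collected, so symptoms of hypo- or hypercalcemia with onset after dosing are recorded as AEs. Do not merely delete the efficacy-data condition: that would leave normal fluctuation or expected progression as the only test and so widen the exemption.

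**Cost.** The SAP part is a short term list and a table row, with no new data. The protocol part is one clarifying sentence. The drawback is that special-interest counts will rise and include some symptoms unrelated to calcium; the sub-row lets a reader separate them.
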